6.14.4. Columbia-Suicide Severity Rating Scale (C-SSRS)

Given that few or no suicidal ideation or behaviors are anticipated, C-SSRS will be listed by patient and visit. Only patients that show suicidal ideation/behavior or self-injurious behavior without suicidal intent will be displayed (i.e., if a patient's answers are all "no" for the C-SSRS, then that patient will not be displayed). However, if a patient reported any suicidal ideation/behavior or self-injurious behavior without suicidal intent at any time point, then all his/her ideation and behavior will be displayed, even if not positive.

The Self-Harm data will be listed by patient and visit if number of events on Self-Harm Supplement Form is not zero in the *Self Harm Questionnaire Supplement* eCRF.

6.14.5. Clinical Laboratory Evaluation

Clinical laboratory assessments include hematology, serum chemistry, urinalysis, and safety-related immune markers such as neutrophil counts.

Continuous laboratory tests will be summarized as changes from baseline to last observation for patients who have both baseline and at least one post-baseline result for the Blinded Treatment Periods, respectively:

- The scheduled visits/measurements will be included. The unscheduled visits and the repeat measurements will be excluded.
- Both international system of units (SI) and conventional units will be summarized when different.
- For the safety population the comparisons between and among treatment groups will be conducted using an ANCOVA with treatment and baseline value in the model.
- Data will be analyzed based on original scale.

Laboratory test observed values at each visit (starting at baseline) and change from baseline to each scheduled visit, respectively, will be displayed in box plots for patients who have both a baseline and at least one post-baseline result. These box plots will be used to evaluate trends over time and to assess a potential impact of outliers on central tendency summaries.

- The scheduled visits/measurements will be included. The unscheduled visits and the repeat measurements will be excluded.

The number and percentage of patients with a treatment-emergent or follow-up emergent abnormal, high, or low for laboratory tests will be summarized by treatment group for each study period. The comparisons between and among treatment groups will be conducted using Fisher's exact test for the safety population for the Blinded Treatment Periods.

- All scheduled, unscheduled and repeated measurements will be included.

- Performing laboratory will be used to define the low and high limits reference range except for leukocyte, neutrophil, lymphocyte and platelet counts, where Lilly defined lower limit of normal will be used for these 4 labs. Alanine aminotransferase (ALT), aspartate aminotransferase (AST), total bilirubin, alkaline phosphatase (ALP), neutrophils, leukocytes, platelets, and lymphocytes will not be included in the treatment-emergent abnormal, high, or low summary as a separate analysis addressing the risk of liver injury is described in Section 6.14.5.1.
- Note that the ranges are defined by a lower limit of normal (LLN) and an upper limit of normal (ULN). A result that is greater than or equal to the LLN and less than or equal to the ULN is considered to be within the normal ranges.
- For categorical laboratory tests:
 - Treatment-emergent abnormal value is defined as a change from normal at all baseline visits to abnormal at any time post-baseline during the treatment period.
 - Follow-up emergent abnormal result is defined as a change from normal at baseline to abnormal at any time during the follow-up period.
- For continuous laboratory tests:
 - Treatment-emergent high value is defined as a change from a value less than or equal to the ULN at all baseline visits to a value greater than the ULN at any time post-baseline during the treatment period.
 - Treatment-emergent low value is defined as a change from a value greater than or equal to the LLN at all baseline visits to a value less than the LLN at any time post-baseline during the treatment period.
 - Follow-up emergent high value is defined as a change from a value less than or equal to the ULN at baseline to a value greater than the ULN at any time post-baseline during the follow-up period.
 - Follow-up emergent low value is defined as a change from a value greater than or equal to the LLN at baseline to a value less than the LLN at any time post-baseline during the follow-up period.

By-patient listing of abnormal laboratory test results (criteria defined in the shift tables excluding the normal category) for parameters of special interest (hepatic, leukocytes and platelets) will be provided.

6.14.5.1. Leukocytes (WBC) and Platelets

Further analyses will be conducted for total leukocytes, neutrophils, platelets, lymphocytes, monocytes, eosinophils, and basophils. Neutrophils is defined as absolute neutrophils (derived by adding segmented neutrophils and band neutrophil).

Shift table will be produced showing the number and percentage of patients shifting from baseline to a minimum post-baseline result in each relevant category by treatment group for the Blinded Treatment Periods:

- Scheduled visits, unscheduled visits, and repeat measurements will be included.
- Baseline is defined as the minimum result during the defined baseline period or baseline.
- Use the minimum non-missing post-baseline value within each study period.
- The parameters and categories are:
 - Leukocytes; $\geq 1 \times \text{LLN}$, $< \text{LLN}$ to $\geq 3.0 \times 10^9/\text{L}$, $< 3.0 \times 10^9/\text{L}$ to $\geq 2.0 \times 10^9/\text{L}$, $< 2.0 \times 10^9/\text{L}$ to $\geq 1.0 \times 10^9/\text{L}$, and $< 1.0 \times 10^9/\text{L}$
 - Neutrophils: (absolute neutrophils); $\geq 1 \times \text{LLN}$, $< \text{LLN}$ to $\geq 1.5 \times 10^9/\text{L}$, $< 1.5 \times 10^9/\text{L}$ to $\geq 1.0 \times 10^9/\text{L}$, $< 1.0 \times 10^9/\text{L}$ to $\geq 0.5 \times 10^9/\text{L}$, and $< 0.5 \times 10^9/\text{L}$
 - Platelets; $\geq 1 \times \text{LLN}$, $< \text{LLN}$ to $\geq 75.0 \times 10^9/\text{L}$, $< 75.0 \times 10^9/\text{L}$ to $\geq 50.0 \times 10^9/\text{L}$, $< 50.0 \times 10^9/\text{L}$ to $\geq 25.0 \times 10^9/\text{L}$, and $< 25.0 \times 10^9/\text{L}$
 - Lymphocytes; $\geq 1 \times \text{LLN}$, $< \text{LLN}$ to $\geq 0.8 \times 10^9/\text{L}$, $< 0.8 \times 10^9/\text{L}$ to $\geq 0.5 \times 10^9/\text{L}$, $< 0.5 \times 10^9/\text{L}$ to $\geq 0.2 \times 10^9/\text{L}$, and $< 0.2 \times 10^9/\text{L}$
- The above LLNs are defined as:
 - Leukocytes: $\text{LLN} = 4.0 \times 10^9/\text{L}$
 - Neutrophils: $\text{LLN} = 2.0 \times 10^9/\text{L}$
 - Platelets: $\text{LLN} = 150 \times 10^9/\text{L}$
 - Lymphocytes: $\text{LLN} = 1.1 \times 10^9/\text{L}$
- With additional categories:
 - Decreased; post-baseline category $<$ baseline category
 - Increased; post-baseline category $>$ baseline category
 - Same; post-baseline category = baseline category.

The change from minimum baseline to minimum post-baseline result for each of these leukocytes and platelets will be summarized graphically using a box plot for the Blinded Treatment Periods:

- All scheduled, unscheduled and repeated measurements will be included.

6.14.5.2. Neutrophil Follow-Up

Neutrophil counts will be followed throughout the study. Patients will continue in Period 4 until their neutrophil counts have recovered.

The neutrophil follow-up analysis will be conducted on the neutrophil follow-up population defined as patients who have an absolute neutrophil count < 1500 cells/ μL (SI units: $< 1.5 \times$

$10^9/L$) at the last scheduled visit or early termination visit prior to entering the Post-Treatment Follow-Up Period and less than the patient's baseline absolute neutrophil count (that is, prior to first injection at Week 0). These patients are monitored during the Period 4 until neutrophil recovery.

Neutrophil clinical recovery is defined as an absolute neutrophil count ≥ 1500 cells/ μL (SI units: $\geq 1.5 \times 10^9/L$) or greater than or equal to a patient's minimum absolute neutrophil count prior to first study drug injection at Week 0.

If a patient's neutrophil count has not recovered, within 12 weeks after entering the follow-up period (Visit 802), the patient will return for Visit 803 (12 weeks after Visit 802). Additional visits may be required for appropriate patient management depending upon the degree of neutropenia. If at Visit 802, a patient's has met the criteria for neutrophil recovery, the patient's participation in the study will be considered complete unless the investigator deems additional follow-up may be necessary.

The number and percentage of patients achieving neutrophil clinical recovery will be presented by treatment group and week interval for neutrophil follow-up population for Post-Treatment Follow-Up Period. The number and percentage of patients with an absolute neutrophil cell count that is at least 25%, 50%, 75%, or 100% of the patient's baseline absolute neutrophil count (that is, prior to first injection at Week 0), irrespective of absolute neutrophil minimum, will be included in the summary.

6.14.6. Vital Signs - Weight

Weight and its change from baseline will be summarized by treatment for safety population at scheduled visits during the Blinded Treatment Periods using descriptive statistics.

6.15. Biomarker Analyses

Refer to a separate SAP addendum for biomarker analyses plan.

6.16. Immunogenicity

6.16.1. Definitions and Terms

The following sample- and patient-related definitions and parameters will be used to describe the immunogenicity data.

[figure not shown]
6.16.1.1. Sample Category Definitions

Samples are classified into the following categories:

- **Unevaluable sample:** Sample could not be tested for anti-drug antibody (ADA) due to sample loss, mishandling, or errors in collection, processing, storage, etc.
- **Antidrug antibody (ADA) Positive sample:** The presences of ADA is detected and confirmed. The samples are reported as positive. If the sample is positive, a titer value is reported.

- **Neutralizing anti-drug antibody (NAb) Positive sample:** NAb are reported as detected.
- **ADA Negative sample:** The presence of ADA is not detected and the assay drug tolerance level is not exceeded.
- **NAb Negative sample:** The presence of NAb is not detected and the assay drug tolerance level is not exceeded.

Inconclusive sample: when ADA/NAb is not detected in a sample but drug is present in the same sample at a level that can cause interference in the ADA/NAb detection method (i.e., above the limit of drug tolerance of the ADA/NAb assay). The upper limit of drug tolerance in the ADA assay is 480.5 µg/mL and the upper limit of drug tolerance in the NAb assay is 1.1 µg/mL. A negative ADA/NAb result cannot be confirmed if drug concentrations present in the testing sample is above the limit of drug tolerance of the assay, and the sample should be considered inconclusive. [Figure RHCR.6.1](#) illustrates the relationship of some of the above terms.

Abbreviation: ADA = anti-drug antibody.

Figure RHCR.6.1. Sample definitions.

[figure not shown]
6.16.1.2. Patient Category Definitions

The following categories are applied to patients based on the classification of their samples:

- **Unevaluable patient:** a) a patient with no evaluable baseline sample and/or no evaluable post-baseline samples; b) a patient with an evaluable baseline sample but no evaluable post-baseline sample; c) a patient with no evaluable baseline sample, but whose evaluable post-baseline values are all ADA positive or a mix of positive and negative. (Note: If all post-baseline samples are negative, the patient is considered ‘evaluable’ and will be classified as ADA-negative.)

- **Evaluable patient:** a) Patient with an evaluable baseline sample and at least 1 evaluable post-baseline sample (that is, sample after administration of study drug); b) patient with no evaluable baseline sample whose evaluable post-baseline samples are all ADA negative.

Figure RHCR.6.2 illustrates the relationship of the above terms.

[figure not shown]
Abbreviation: ADA = anti-drug antibody.

Figure RHCR.6.2. Patient categories (evaluable/unevaluable) based on sample status at baseline and post-baseline.

6.16.1.3. Definitions for Clinical Interpretation of Assay Results

- **Baseline:** For immunogenicity analyses, baseline is the last nonmissing observation on, or prior to, the date of the first injection of study treatment of ixekizumab (Week 0).
- **Baseline ADA positive (preexisting antibody):** ADA detected in a sample collected at baseline.
- **TE-ADA positive:** a) a patient with a ≥ 4 -fold (or 2 dilutions) increase over a positive baseline antibody titer; or b) for a negative baseline titer, a patient with an increase from the baseline to a level of $\geq 1:10$.
- **Baseline ADA-negative:** ADA is not detected in a sample collected at baseline.
- **TE-ADA inconclusive patient:** A patient without a TE-ADA positive sample and with at least 1 sample for which drug levels may interfere with the ADA assay.
- **TE-ADA negative patient:** A patient who is evaluable for TE-ADA and is not either TE-ADA positive or TE-ADA inconclusive.

Figure RHCR.6.3 illustrates the relationship of some of these terms.

Abbreviation: ADA = anti-drug antibody.

Figure RHCR.6.3. Relationship of terms for clinical interpretation of assay results for evaluable patients.

- **Incidence of TE-ADA:** Patients with TE-ADA as a proportion of the evaluable patient population during the treatment period. This excludes unevaluable patients.

[figure not shown]
All ADA positive samples will be evaluated for NAb. NAb patient status will be defined as follows:

- **NAb-positive patient:** A patient where a NAb positive result is detected for ≥ 1 TE-ADA positive samples.
- **NAb-inconclusive patient:** A patient without a NAb positive sample and with at least 1 sample for which drug levels may interfere with the NAb assay.
- **NAb-negative patient:** A patient who is evaluable for NAb and is not either NAb positive sample or NAb inconclusive.

ADA and TE-ADA titer values will be categorized as follows:

- Low Titer if titer value (LOCF) $< 1:160$;
- Moderate Titer if titer value (LOCF) $\geq 1:160$ and $< 1:1280$; and
- High Titer if titer value (LOCF) $\geq 1:1280$.

A flow chart that reflects the connection between the analytical test results and the clinical interpretation based on the definitions is shown in [Figure RHCR.6.4](#).

Abbreviation: ADA = anti-drug antibody.

Figure RHCR.6.4. Flow chart of ADA assessment with clinical interpretation of the various result possibilities.

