- c To be performed if not done in the prior 6 months.
- d Patients who test positive for latent TB at screening may be re screened following appropriate treatment. Additionally, patients who do not qualify at baseline under Exclusion Criterion [34] (active or recent infection) may be re-screened (1 time).
- e See [Table RHCR.7.1](#). All patients should remain under observation for at least 1 hour after study drug administration to monitor safety at Week 0.
- f Designated Unblinded Site Personnel will be responsible for handling and dispensing of all study drugs (ixekizumab, guselkumab, and placebo).
- g Administered only to patients with PsA at the baseline (W0) visit.
- h To be completed only by patients with PsA at the baseline (W0) visit.
- i Patients who test positive for latent TB at screening may be re-screened. QuantiFERON® may be performed by a Lilly-designated or local laboratory. See [Section 9.4.4](#) for detailed description of QuantiFERON®-TB Gold .
- j FSH test performed for women  $\geq 40$  and  $< 60$  years of age who have had a cessation of menses for at least 12 months to confirm non-childbearing potential ( $\geq 40$  mIU/mL).
- k All patients will be tested for HBV at screening. Patient who meet criteria for HBV monitoring (see [Section 9.4.6.3](#)) will be identified by the central laboratory at baseline and monitored according to the study schedule.
- l To be performed for females of childbearing potential only. Additional urine pregnancy testing can be performed at the investigator's decision. Patients determined to be pregnant will be discontinued from treatment and will no longer be administered study drug.
- m To be performed for females of childbearing potential only. Patients determined to be pregnant will be discontinued from treatment and will no longer be administered study drug.
- n To analyze change from baseline, the immunogenicity sample collected at baseline (W0) will be used. For any patient who experiences a potential systemic allergic/hypersensitivity reaction during the study as judged by the investigator, a sample will also be collected when possible to be tested for immunogenicity and PK. Samples from patients treated with guselkumab will not be analyzed for anti guselkumab antibodies. These samples will be discarded at the end of the study.

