### **7.1.2. Observations after Study Drug Administration**

All patients should remain under observation for at least 1 hour after study drug administration to monitor safety at Week 0.

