### 9.4.2. Immunogenicity Assessments

Samples for immunogenicity testing including a pharmacokinetic sample will be collected at Visit 2, and at later time points in case of event judged by the investigator to be a potential systemic allergic/hypersensitivity reaction, when possible. Venous blood samples (approximately 10 mL) will be collected in tubes and used to determine antibody production against ixekizumab. The actual date of each sampling will be recorded on the laboratory requisition. To analyze change from baseline, the exploratory sample collected at Visit 2 will be used. If analyzed, the samples will be evaluated in validated immunogenicity assays at an external vendor in a screening assay and if positive a neutralizing ADA assay. Assay validation details are available upon request.

Samples from patients treated with guselkumab will not be analyzed for anti-guselkumab antibodies. These samples will be discarded at the end of the study. Immunogenicity will be assessed by a validated assay designed to perform in the presence of ixekizumab. Antibodies may be further characterized and/or evaluated for their ability to neutralize the activity of ixekizumab. Samples will be retained for a maximum of 15 years after the last patient visit or for a shorter period if local regulations and ERBs allow, at a facility selected by the sponsor, to enable further analysis of immune responses to ixekizumab. This duration will allow the sponsor to respond to regulatory requests related to the study drug. Any samples remaining after 15 years will be destroyed.

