### 10.3. Statistical Analyses

#### 10.3.1. General Statistical Considerations

Statistical analysis of this study will be the responsibility of Lilly.

Continuous data will be summarized in terms of the mean, standard deviation, minimum, maximum, median, and number of observations. Categorical data will be summarized as frequency counts and percentages.

Unless otherwise specified, efficacy, and health outcome analyses will be conducted on the ITT population. This set includes all data from all randomized patients according to the treatment the patients were assigned, regardless of whether they received the treatment or not.

The randomization to treatment groups is stratified by site as described in Section 7.2. Study sites with fewer than 5 randomized patients per treatment group will be pooled for statistical analysis purposes. All efficacy and health outcomes analyses will use pooled sites.

All tests of treatment effects will be 2-sided, unless otherwise stated.

The Induction Dosing Period (Period 2) starts at the first injection of study drug at Week 0 (Visit 2) and ends prior to the first injection of study drug at Week 12 or the ETV (between Weeks 0 and 12).

Baseline will be defined as the last available value before the first injection for efficacy, health outcomes, and safety analyses. In most cases, this will be the measure recorded at Week 0 (Visit 2). For efficacy measures, if the patient does not take any injection, the last available value on or prior to the randomization date will be used. Change from baseline will be calculated as the visit value of interest minus the baseline value. For safety analyses using a baseline period, the baseline period is defined as the time from Visit 1 to the date/time of the first injection.

The primary analysis method for treatment comparisons of categorical efficacy, health outcomes variables at specific time points will be made using a Cochran-Mantel-Haenszel (CMH) test stratified by pooled site. Missing data will be imputed using the nonresponder imputation (NRI) method. The 95% confidence interval (CI) associated with the treatment response rate, and treatment difference will be provided. Secondary analysis will be conducted using a Fisher's exact test.

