6.1.2. Baseline Definition

For the Blinded Treatment Periods, the baseline value will be defined as the last available value before the first treatment injection for both efficacy/health outcomes and safety analyses. In most cases, this will be the measure recorded at Week 0 (Visit 2). For efficacy/health outcome measures, if the patient does not take any injection, the last available value on or prior to randomization date will be used.

Change from baseline will be calculated as the postbaseline value minus the baseline value. Percent change from baseline is defined as: 100 times the change from baseline divided by baseline). Percent improvement from baseline is calculated as: the positive percent change from baseline if a higher value postbaseline means improvement from baseline; and as the negative percent change from baseline if a lower value postbaseline means improvement from baseline. If the baseline value is missing for a particular variable, then the change from baseline and the percent improvement from baseline will not be calculated.

For safety analyses using a baseline period, the baseline period is defined as the time from Visit 1 to the date/time of the first injection.

For the Post-Treatment Follow-Up Period, the baseline is defined as the last nonmissing assessment on or prior to entering Period 4, that is, on or prior to Week 24 (Visit 12), or at the early termination visit (ETV).

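### SAP 6.16.1.3 sets the immunogenicity baseline by date and not by time of first injection, so a reaction sample drawn after the Week 0 dose qualifies as baseline

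*SAP*

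**What the plan says.** SAP 6.16.1.3 gives immunogenicity its own baseline: "baseline is the last nonmissing observation on, or prior to, the date of the first injection of study treatment of ixekizumab (Week 0". It uses no time of day.

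Other parts of the documents use a different rule or name a specific sample:

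- SAP 6.1.2, for the Blinded Treatment Periods: "the baseline value will be defined as the last available value before the first treatment injection".
- Protocol 10.3.1: "Baseline will be defined as the last available value before the first injection".
- Protocol Schedule of Activities, footnote n: "To analyze change from baseline, the immunogenicity sample collected at baseline (W0) will be used". Protocol 9.4.2 likewise names the Visit 2 sample, and protocol 10.3.5 compares a reaction sample with a stored baseline sample where possible.

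SAP 6.16.1.2 decides who can be analysed. An evaluable patient normally needs an evaluable baseline sample and "at least 1 evaluable post-baseline sample (that is, sample after administration of study drug". One of the unevaluable categories is "a patient with an evaluable baseline sample but no evaluable post-baseline sample".

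On collection, the Schedule of Activities has routine immunogenicity sampling at Week 0 only. Any other sample is triggered by a potential systemic allergic or hypersensitivity reaction and is to be taken promptly (protocol 7.9.2 and 9.2.1.2). At the first dose, protocol 7.1.2 adds: "All patients should remain under observation for at least 1 hour after study drug administration to monitor safety at Week 0". On what is recorded, protocol 9.4.2 says: "The actual date of each sampling will be recorded on the laboratory requisition".

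**The concern.** A patient who reacts after the Week 0 dose can have two immunogenicity samples on one calendar date: the scheduled one before dosing and the reaction one after it. A rule that accepts anything on the date of first injection and takes the last value selects the post-dose sample. The sample that was meant to be tested against baseline then becomes the baseline.

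The SAP is careful about clock time elsewhere. The safety baseline period in 6.1.2 ends at the date and time of first injection, and 6.14.2 uses date and time to decide whether an adverse event is treatment-emergent. The immunogenicity rule is the exception.

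The stake is the classification of individual patients. Post-baseline samples come only from suspected reactors, so the TE-ADA denominator is restricted to them and each patient carries weight. The same rule also decides who is labelled as having pre-existing antibody.

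**Working it through.** The documents give no count, incidence or power figure for the immunogenicity analysis, so there is no stated figure to reproduce. The check applies the SAP definitions to possible sets of samples.

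**Inputs**

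- Baseline as written: last nonmissing sample on or before the date of first injection (SAP 6.16.1.3).
- TE-ADA positive: at least a 4-fold rise over a positive baseline titre, or a rise to at least 1:10 from a negative baseline (SAP 6.16.1.3).
- Evaluable and unevaluable patients: SAP 6.16.1.2.
- The scheduled Week 0 sample is pre-dose, because protocol 7.3.1 puts scheduled assessments before the injection.

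**Step 1: which sample is baseline?** Call the scheduled pre-dose sample S and the Day 0 reaction sample R. Both carry the date of first injection, and R is the later of the two. As written, R is the baseline.

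**Step 2: is there a post-baseline sample?** Suppose no further sample is taken. The SAP allows two readings.

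- Reading 1: post-baseline means later than the baseline sample. Nothing is later than R, so the patient is unevaluable.
- Reading 2: post-baseline means after study drug, the gloss in SAP 6.16.1.2. R is then both baseline and post-baseline. The titre ratio is R/R = 1, below 4, and a negative R stays negative. TE-ADA positivity is impossible.

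**Step 3: compare with a pre-dose baseline.** The titres below are hypothetical.

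| Samples | As written, reading 1 | As written, reading 2 | Pre-dose baseline (either reading) |
|---|---|---|---|
| S negative, R negative | Unevaluable | TE-ADA negative | TE-ADA negative |
| S negative, R 1:10 | Unevaluable | TE-ADA negative | TE-ADA positive |
| S negative, R negative, Day 28 1:40 | TE-ADA positive | TE-ADA positive | TE-ADA positive |
| S negative, R 1:20, Day 28 1:40 | TE-ADA negative (40/20 = 2-fold) | TE-ADA negative | TE-ADA positive |
| S negative, reaction on Day 14 only, 1:40 | TE-ADA positive | TE-ADA positive | TE-ADA positive |

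Patients first sampled for a reaction after Day 0 are not affected. Where S and R give the same antibody result, reading 2 and the later-sample case classify the patient as a pre-dose baseline would. Reading 1 still loses the patient who has no later sample.

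**Step 4: direction of any effect.** Assume, for illustration only, 20 sampled ixekizumab patients of whom 4 are TE-ADA positive against a pre-dose baseline: 4/20 = 20.0%.

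- If 1, 2 or 3 negative patients have only a Day 0 reaction sample, reading 1 gives 4/19 = 21.1%, 4/18 = 22.2% or 4/17 = 23.5%. Reading 2 leaves 4/20 = 20.0%.
- If instead one of the 4 positive patients has only a Day 0 reaction sample, reading 1 gives 3/19 = 15.8% and reading 2 gives 3/20 = 15.0%.

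The figure can rise, stay the same or fall.

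**The case against.** The strongest reply is that the intended comparison is clear from the protocol: the scheduled Visit 2 sample against the reaction sample. Footnote n and sections 9.4.2 and 10.3.5 all point that way, and 9.4.2 describes reaction samples as coming at later time points. On this view the SAP sentence is loose drafting. That stands as evidence of intent. It does not remove the defect, because the SAP definition is the one that would be programmed and it gives a different comparator.

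Four stronger readings are tempting, and the documents do not support them.

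- A reader might infer that such a patient always drops out as unevaluable. That needs both the absence of a later sample and a reading of post-baseline that sets aside the SAP's own gloss.
- A reader might infer that TE-ADA incidence is inflated. That follows only under reading 1, and only if the lost patients are TE-ADA negative.
- A reader might infer that the order of same-day samples cannot be recovered. Protocol 9.4.2 says that the date is recorded; it does not say that the time is omitted, and the requisition is not among the documents. One sample is also scheduled and the other reaction-triggered, and dose time is recorded under protocol 7.3.1.
- A reader might infer that drug in the post-dose sample would spoil the antibody result. Protocol 9.4.2 describes an assay designed to work in the presence of ixekizumab, and SAP 6.16.1.1 gives a tolerance of 480.5 µg/mL. To reach that level, the whole 160 mg starting dose would have to be contained in 160,000/480.5 = 333 mL. The neutralizing assay tolerates only 1.1 µg/mL, but it is applied only to antibody-positive samples.

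The narrow scope is also a fair point. Testing of these samples is conditional, guselkumab samples are not analysed, and SAP 6.16 specifies no between-group test.

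**Conclusion.** The point holds as an error in a stated definition. SAP 6.16.1.3 conflicts with SAP 6.1.2, with protocol 10.3.1 and with the comparison that the protocol intends. For an ixekizumab patient sampled for a suspected systemic reaction after the Week 0 dose, it makes the post-dose sample the baseline. The patient is then unevaluable or compared with the same sample if there is no later one, and measured against the wrong comparator if there is.

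The size is unknown. The documents give no reaction rate and no share of reactions on Day 0, so the percentages shown are arithmetic on assumed counts and neither a loss of patients nor an upward bias is established. No efficacy analysis is touched. The severity is minor, and the case for acting is that the wording is wrong and the correction is easy.

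**What to change.** In SAP 6.16.1.3, define the immunogenicity baseline as the last evaluable sample collected before the date and time of the first injection, in practice the scheduled pre-dose Visit 2 sample. State there, consistently with SAP 6.16.1.2, that every sample collected after the first injection is post-baseline, including one taken on the same day. With that wording, a patient with a pre-dose sample and a Day 0 reaction sample is evaluable and is compared with the pre-dose sample under either reading.

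Check whether the laboratory requisition captures collection time, and add the field if it does not, so that the order of same-day samples rests on recorded data.

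The cost is one amended SAP definition and at most one additional requisition field. No extra blood draw or visit is needed.
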